8.8.2. Secondary outcome measures

	Secondary Outcome Measures
Outcome 1: Exclusive Breastfeeding at day 28 of birth.	Description: Exclusive breastfeeding is defined as feeding an infant with only breast milk and no additional food, water, or other liquids (with the exception of medicines and vitamins, if needed). This will be assessed on Day 29 follow up visit using 24 hour dietary recall method for exclusive breastfeeding. Exclusive breastfeeding will be measured in a manner consistent with the Infant and Young Child Feeding indicators recommended by WHO and UNICEF.
Outcome 2: Score on the Breastfeeding Experience	Description: The Breastfeeding Experience Scale is a 19-point scale of potential negative experiences that the mother may have had

Scale as reported by mother on follow-up day 8 to assess early challenges with breastfeeding.	since birth (e.g., sore nipples and other breast-related problems, infant-related challenges to breastfeeding success, mother's own perceptions and anxiety, etc.), and the degree to which those experiences posed a challenge to breastfeeding.
	We will aim to compare both the score on the number of negative experiences as well as the degree to which these experiences influenced breastfeeding between the intervention and control groups.
Outcome 3: Possible Serious Bacterial Infection (PSBI) among infants on follow-up days (days 4, 8, 15 and 29).	 Description: Possible serious bacterial infection commonly known as PSBI is defined as the presence of any of the following clinical signs in the infants: Convulsions Not able to feed at all No movement at all Low body temperature (< 35.5°C) Not feeding well Movement only when stimulated Severe chest indrawing High body temperature (38°C or above) Fast breathing (60 breaths per minute or more) in infants < 7 days The PSBI signs will be assessed by trained and standardised workers during follow-up visits as per IMNCI assessment protocol on days 4, 8, 15 and 29.
Outcome 4: Maternal	Description:
depression measured at 15days after birth.	 The Edinburgh Postnatal Depression Scale (EPDS) The scale consists of 10 short statements. Responses are scored 0, 1, 2 and 3 based on likert scale. Items 3, 5 to 10 are reverse scored (i.e., 3, 2, 1, and 0). The total score is calculated by adding together the scores for each of the 10 items. Mothers scoring above 13 will be considered as suffering from depression. The EPDS will be administered by trained and standardised workers
	on the follow-up day 15 visit.
Outcome 5: Mother-to-infant bonding scale measured on day 29.	Description: The Mother-to-infant Bonding Scale (MIBS) The scale was developed in London and consists of 8 different self- reported feelings of mothers towards their babies, and aims to assess how often mothers experience these feelings towards their babies. Each of the 8 items is scored on a 0-3 Likert scale. The total score is calculated by adding together the scores of the 8 items. It is reverse-scored - so a low score indicates better attachment and a high score indicates worse attachment. There is a slight variation of this scale validated in the Japanese context, consisting of 10 items. We may use the latter scale, given that it is from an Asian context. The MIBS will be administered to mothers on follow-up day 29 visit.
Outcome 6: Breastfeeding	Description:
self-efficacy scale (short form) measured on day 29.	The Breastfeeding Self-Efficacy Scale-Short Form (BSES-SF) The Breastfeeding self-efficacy scale was developed to assess maternal confidence in breastfeeding to identify mothers at risk of weaning as well as evaluate the effectiveness of various interventions in supporting breastfeeding. It consists of 14 items scored on a 5- point Likert scale, where 1 indicates 'not at all confident' and 5

indicates 'always confident'. The total score is calculated by adding together the scores on all 14 items.
The BSES-SF will be administered to mothers on follow-up day 29 visit.

Other outcome measures (sub-sample)						
Mechanistic sub-study						
Duration of hypothermia (axillary temperature < 36.5°C) over the first 48 hours of life.	Description: Continuous ambulatory temperature monitoring of the newborn will be done to compare hypothermia prevalence in infants of both groups using validated sensors (device to be decided).					
This will be assessed in a sub- sample of 40 newborns each in the intervention and control groups as part of a mechanistic sub-study.	Hypothermia is classified into three grades: Mild (36.0°C – 36 .5°C), moderate (32.0°C – 35.9°C), and severe (<32.0°C) hypothermia. The total duration of time when the device records a temperature < 36.5°C will be measured over the first 48 hours for every infant.					
Heart rate variability during the first 48 hours of life. This will be assessed in a sub-	Description: Continuous heart rate monitoring of the newborn will be done over the first 48 hours using a pulse oximeter (plethysmograph, device to be decided).					
sample of 40 newborns each in the intervention and control groups as part of a mechanistic sub-study.	Heart rate variability for various time intervals (first 6 hours, 6-24 hours, 24-48 hours) will be calculated using standard techniques. Heart rate variability in newborns is associated with stress as well as human touch and maternal-infant synchrony. ³⁰⁻³²					

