6.2. Secondary objectives

- **6.2.1.** To compare the proportion of infants who are exclusively breastfed during the first 3 days and at age 28 days between the intervention and control groups.
- **6.2.2.** To compare experiences of mothers related to breastfeeding success using the Breastfeeding Experience Scale and Breastfeeding Self-Efficacy Scale between the intervention and control groups
- **6.2.3.** To compare the incidence of possible serious bacterial infection (PSBI) between the intervention and control groups during the first 28 days of life

- **6.2.4.** To compare the incidence of maternal depression among mothers in the intervention and control groups
- **6.2.5.** To compare the Maternal-Infant Bonding Scale (MIBS) scores among mothers in the intervention and control groups

7. KEYWORDS:

Kangaroo Mother Care; intrauterine-to-extrauterine transition; physiological care; breastfeeding; early weight loss; weight gain.

8. METHODOLOGY:

The study methodology is written according to the Standard Protocol Items: Recommendations for Interventional Trial Statements (SPIRIT)¹

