8.8. Outcomes, assessment and measurement

8.8.1. Primary outcome measures

	Primary Outcome Measures
Outcome 1: Percentage weight change over the first 48 hours after birth.	Description: Percentage weight change over the first 48 hours after birth is defined as:
	$\frac{Weight taken at (48 \pm 6) hours - Birth weight}{Birth weight} \times 100$
	All singleton infants will be weighed by workers trained and standardised in anthropometry assessments using a calibrated Seca 334 or equivalent digital weighing scale, accurate to ± 5 grams.
Outcome 2: The weight gain velocity during the newborn	Description: Weight gain velocity will be calculated as:
period	$\frac{Weight at ady n - Birth weight}{Birth weight} \times \frac{1}{n} \times 100$
	where n is the completed age of the baby at last follow-up, between 28-32 (included)
Outcome 3: Quality of	Description:
breastfeeding as measured through the Bristol Breastfeeding Assessment Tool (BBAT) score on Day 8 (i.e. at 7 completed days of	The BBAT assessment assigns numerical scores (0, 1, or 2) to four key breastfeeding components (position, attachment, sucking and swallowing) and summarising to a scale-score between 0-8, with a higher rating indicating better breastfeeding performance.
age).	The BBAT score is categorised into 3 categories: poor (0-2), moderate (3-6) and good (7-8).

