8.10. Severe adverse events (SAEs)

The following have been identified as reportable SAEs:

Newborns

- Newborn death
- Admission to a Level-2 or above newborn care unit

During the postnatal stay of the mother-newborn dyad, newborns will be under round-the-clock monitoring of the hospital team. Newborn deaths and admission to neonatal intensive care will be notified to the study team, and documented using the SAE forms. During post-discharge follow-up, SAEs will be documented by study evaluation workers on visit days based on information and records provided by the family.

Upon identification of an SAE, it will be verified and notified within 24 hours by the Principal Investigator to the data and safety monitoring board (DSMB). All SAEs will also be communicated to the ethics committee on a monthly basis.

A masked interim analysis will be performed by the DSMB to review the safety of the trial once 50% of participants have completed the follow-up, where relative incidence rates and severity of events in the two arms will be compared.

Due to the low-risk nature of the study, no stopping rules have been defined.

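### The PSBI objective asks for incidence over 28 days, but the outcome counts only signs present at four visits and is not linked to the admissions and deaths recorded as SAEs

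*Protocol*

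**What the plan says.** The objective (Protocol, section 6.2.3) reads: "To compare the incidence of possible serious bacterial infection (PSBI) between the intervention and control groups during the first 28 days of life".

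The matching outcome (section 8.8.2, Outcome 3) is PSBI "among infants on follow-up days (days 4, 8, 15 and 29". A case is "defined as the presence of any of the following clinical signs in the infants", and the signs are "assessed by trained and standardised workers during follow-up visits as per IMNCI assessment protocol on days 4, 8, 15 and 29". One sign is limited by age: "Fast breathing (60 breaths per minute or more) in infants < 7 days".

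The schedule in section 8.11 places the PSBI module at the same four visits and not on D1 or D2.

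Section 8.10 lists newborn death and "Admission to a Level-2 or above newborn care unit" as reportable SAEs. After discharge these are picked up at the visits: "During post-discharge follow-up, SAEs will be documented by study evaluation workers on visit days based on information and records provided by the family". Neither section 8.8.2 nor section 8.10 links these records to PSBI, and no current secondary outcome covers admission or death.

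**The concern.** Incidence over an interval and presence of signs on chosen days are different quantities. The first counts every infant who becomes a case at any time in the 28 days. The second counts infants who are symptomatic when the assessor is there. Under the written definition, an infant whose signs appear on day 18 and are gone by day 22 is not a PSBI case. Nor does an admission or a death between visits make an infant a case, even when serious infection was the reason.

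Two things are at stake. A result labelled as 28-day incidence would be too low in both arms. The trial's only infection outcome would also rest on fewer events than occurred, so its comparison would be less precise than the follow-up allows.

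The protocol itself fixes both the definition and the collection points. An analysis plan could later link SAE records to the outcome. It could not recover a sign that was never asked about, or a cause of admission that was never recorded.

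**Working it through.** The protocol states no PSBI rate, effect size or power, so there is no figure of its own to reproduce. The check is how much of the 28-day window four visits can see.

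**Visit spacing.** Section 8.8.1 fixes the day numbering: the BBAT is a "score on Day 8 (i.e. at 7 completed days of" age. Days 4, 8, 15 and 29 are therefore 3, 7, 14 and 28 completed days, and the gaps are 3, 4, 7 and 14 days. The last gap is half the window (14/28 = 50%) and has one visit, at its end.

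**Share of episodes seen, uniform onset (assumed).** An episode with signs lasting d days is seen if a visit falls within those d days. In each gap, the onset times that qualify span min(d, gap).

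- Visits at completed ages: share = [min(d,3) + min(d,4) + min(d,7) + min(d,14)] / 28.
- Visits half a day later (3.5, 7.5, 14.5 and 28.5 days), onset uniform over 0 to 28 days: the first gap becomes 3.5 days, and the last visit contributes d − 0.5 because onset stops at day 28.

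| Sign duration (assumed) | Completed ages | Mid-day visits | Mid-day visits, early onset |
|---|---|---|---|
| 2 days | 8/28 = 29% | (2 + 2 + 2 + 1.5)/28 = 27% | 37% |
| 3 days | 12/28 = 43% | (3 + 3 + 3 + 2.5)/28 = 41% | 59% |
| 5 days | 17/28 = 61% | (3.5 + 4 + 5 + 4.5)/28 = 61% | 82% |
| 7 days | 21/28 = 75% | (3.5 + 4 + 7 + 6.5)/28 = 75% | 92% |

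The last column assumes exponential onset with mean 7 days, truncated at 28 days. Capture is higher there because the early visits are closer together. The placing of the visit within the day hardly matters.

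**Age-limited sign.** Fast breathing counts only below 7 days, and an on-schedule Day 8 visit falls at 7 completed days. On schedule, that sign can be scored only at the Day 4 visit.

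**What this does to the comparison.** Let s be the share seen, equal in both arms, with negligible false positives. The observed risks are s·p0 and s·p1. Their ratio is still p1/p0, but their difference shrinks to s·(p0 − p1) and the event count falls by the factor s.

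As an illustration, assume a true control risk of 10%, a risk ratio of 0.5, and the protocol's 244 evaluable infants per arm (section 8.9), using the completed-age shares. Power is the two-sided 5% normal approximation, Φ{(p0 − p1 − 1.96·√[2p̄(1 − p̄)/n]) / √[(p0(1 − p0) + p1(1 − p1))/n]}, where p0 and p1 are the observed risks and p̄ is their mean.

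- All episodes counted: 244 × 0.10 = 24.4 control events, power 0.56.
- 7-day signs: 24.4 × 0.75 = 18.3 events, power 0.44.
- 3-day signs: 24.4 × 12/28 = 10.5 events, power 0.27.

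With an assumed control risk of 5%, full capture gives power 0.31 and 3-day signs give 0.15. At 15% the figures are 0.75 and 0.38. These ignore the design effect of 2.0 in section 8.9; applying it would lower them further.

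**The case against.** **The instruments are not shown.** The PSBI module and the IMNCI procedure are cited but not reproduced, and convulsions or poor feeding could be taken by history. This stands as a caution. However, the written definition is presence of signs on named days. Elsewhere the protocol does state a recall period when it wants one: the Breastfeeding Experience Scale covers the time since birth.

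**Between-visit cases are scored as non-events.** A reader might infer this, but the protocol does not say it. An infant who has died or is in hospital on a visit day could be treated as missing, and section 8.14 leaves details to an analysis plan not shown here. Nor does it say that an infant in hospital goes unassessed. What holds is narrower: such an episode meets no PSBI criterion as written.

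**The most severe cases are lost.** This too would go too far. Deaths and Level-2 or higher admissions are recorded as SAEs and compared by arm at the interim review (section 8.10). They are outside this outcome, not outside the trial. Only episodes managed without such an admission have no stated capture.

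**The comparison is biased.** The documents do not show this. Visit days and module are the same in both arms and the outcome assessors are masked (sections 8.5 and 8.11). With equal capture the expected risk ratio is unchanged. Bias would need KMC, or the extra calls to intervention families (section 8.6), to change how long signs last or when care is sought. That is possible but unsupported.

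**Family-reported episodes could do harm.** Mothers know their allocation, so adding their reports to the main definition could introduce differential reporting that masked assessment avoids. This objection stands, and the fix below respects it.

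**Conclusion.** The mismatch holds. Section 6.2.3 asks for 28-day incidence; section 8.8.2 and the schedule deliver prevalence of signs at four visits, with half the window resting on one of them. Under uniform onset the visits catch about 27% to 75% of episodes lasting 2 to 7 days; under early onset, 37% to 92%. Duration, onset pattern, control risk and effect size are all assumptions, so the direction (understatement) is firm and the size is not.

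The main consequence is lost precision. PSBI is one of six secondary outcomes and has no stated power. The sample size and the primary outcomes are unaffected. The point should be corrected but does not threaten the trial.

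**What to change.** **Preferred change.** In section 8.8.2, define Outcome 3 per infant as either of the following by the Day 29 visit:

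- any listed sign at a visit; or
- a Level-2 or higher newborn-unit admission, or a death, between visits due to possible serious infection, taken from the SAE records.

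Record the cause on the SAE form if it is not already there, and have it classified by someone masked to group.

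Add two sensitivity analyses: visit-day signs alone, and visit-day signs plus signs the family reports since the last visit. The second stays out of the main definition because mothers know their allocation.

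**Minimum alternative.** Restate objective 6.2.3 as PSBI signs at scheduled visits, and do not report the result as 28-day incidence.

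**Cost.** The preferred change needs revised outcome wording, possibly a cause field on the SAE form, masked classification of those SAEs, and one question in the existing PSBI module if it is not already asked. Admissions and deaths are already collected. Attributing cause adds some misclassification, and admission can depend on care-seeking in an open-label trial. Short episodes managed without admission would still be missed by the main definition, so full capture should not be claimed. The minimum alternative costs only wording, but gives up the incidence question.

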8.9. Sample size

Assuming that unexposed newborn infants born with normal birth weight lose an average of 6% (SD 3.6%) of their birth weight within the first 2 days of life (based on a previous pilot study in community settings), in order to detect a 25% reduction in early weight loss at 95% confidence level and 90% power, and a design effect of 2.0, we will need 244 infants in each group, i.e., ~122 infants per group in each facility.

n =
$$((Z_{\alpha/2}+Z_{\beta})^2 * 2^*\sigma^2 / d^2) \times DE$$

where Za/2 is the critical value of the Normal distribution at a/2 (e.g. for a confidence level of 95%, a is 0.05 and the critical value is 1.96), Z β is the critical value of the Normal distribution at β (e.g. for a power of 90%, β is 0.1 and the critical value is 1.28), σ 2 is the population variance, and d is the difference between the two groups (25% of 6% = 1.5%). DE is the design effect assumed to be 2.0. Assuming a loss to follow up of 5%, we will need to enroll 129 infants per group in each facility, i.e. 258 infants in both groups per facility, giving a total sample size of 516 normal birth weight infants.

This sample size will allow us to detect a 20% improvement in cumulative weight gain at age 28 days at 95% confidence level and 80% power (assuming an average increase of 25%, SD 10% in birth weight in control infants). It will also allow us to detect a 50% reduction in mother-baby dyads with a low-moderate BBAT score of < 7 in the intervention arm as compared to control arm at 95% confidence level and 80% power (assuming 30% of dyads in the control group have a BBAT score of < 7).

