8.1. Study design

This is a multicenter, pragmatic, individually randomised controlled, open-label superiority trial, comparing two parallel groups of normal birthweight infants, (weighing \geq 2500 grams at birth) - early and prolonged KMC for the first 72 hours after birth (intervention group) WITH standard care (control group). The unit of randomisation is the mother-infant dyad in a 1:1 ratio.

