8.5. Randomisation, allocation and recruitment

This is an open-label individually randomised controlled study. The study biostatistician will generate a randomisation scheme with random permuted blocks of variable sizes between 2 to 6 using a computer program for each facility. The random allocation file for each facility will be electronically stored in the secure RedCap application database. During the enrolment process after securing informed written consent, the application will automatically assign the infant to the study group corresponding to the next sequence number and record the assigned group in the database, without making it visible in the case report forms. The study nursing team who will be conducting the screening and enrolment, will be able to access the study group assigned to enrolled infants. The study nursing team will also be responsible for overall strengthening of care in the study facilities, and will be referred to as the Screening, Enrolment and Systems Strengthening (SESS) team.

As an open-label trial, the SESS team, the intervention team (known as the 'KMC team'), and the participants will be aware of the assigned study group. However, special measures will be taken to reduce the risk of bias. The independent outcome assessment (IOA) team will be masked to the group allocation. The SESS team will ensure that a common minimum package of care is provided similarly to mother-baby dyads in both the study groups (please see section 8.7). Quality control measures will be adopted to ensure that the standard operating procedures are being duly followed and any deviation from the protocol will be documented. Measures to reduce the risk of bias will include standardised data collection in both the groups with well-defined monitoring and quality protocols.

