8.14. Statistical analysis

The detailed analysis plan based on the following high-level plan will be finalized a priori before initiating any analysis of the study data. Statistical analysis will be conducted using R or STATA.

Baseline characteristics will be compared between the intervention and control groups using independent samples t-tests for continuous variables and chi-square tests or Fisher's exact tests for categorical variables. This will help ensure that randomization has successfully balanced potential confounders across groups.

For the primary outcomes of average weight loss and weight gain as a proportion of birth weight, twosided independent samples t-tests will be used. The standardised effect size will be calculated using Cohen's d. A 95% confidence interval for the mean difference will be calculated. A p-value of <0.05 will be considered statistically significant. Multivariable regression analysis will be employed to adjust for potential confounders, such as birth weight, maternal age, socioeconomic status, etc. Stratified analysis will be conducted to assess the effect of KMC within each hospital. Sensitivity analysis will be conducted to assess the robustness of the results.

Analysis of secondary outcomes will be conducted based on the type of variable. For outcomes such as exclusivity of breastfeeding and perceived milk sufficiency, chi-square tests will be used, and odds ratios with 95% confidence intervals will be calculated. For outcomes measured on an ordinal scale, such as the severity of maternal depression, Kruskal-Wallis tests will be used, and cumulative odds ratios or proportional odds ratios with 95% confidence intervals will be calculated. For continuous outcomes, such as the duration of moderate to severe hypothermia, two-sided independent samples t-tests will be used, and mean differences or median differences with 95% confidence intervals will be calculated.

Masked interim analysis will be conducted for the DSMB upon completion of 50% sample size.

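### The sample size is doubled by an unexplained design effect of 2.0 that the individually randomised design and the planned t-tests do not match; the 80% power for weight gain is understated either way

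*Protocol*

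**What the plan says.** Protocol 8.1 describes the design: "This is a multicenter, pragmatic, individually randomised controlled, open-label superiority trial". It adds "The unit of randomisation is the mother-infant dyad in a 1:1 ratio". Section 8.3 restricts enrolment to singletons. Section 8.5 generates allocation with "random permuted blocks of variable sizes between 2 to 6 using a computer program for each facility", so both arms are present in both hospitals.

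Section 8.9 sizes the trial on early weight loss. It assumes that control infants "lose an average of 6% (SD 3.6%) of their birth weight within the first 2 days of life" and sizes the trial "in order to detect a 25% reduction in early weight loss at 95% confidence level and 90% power". The printed formula is the usual one for two means, multiplied at the end by DE, with the explanation "DE is the design effect assumed to be 2.0". The result is 244 per group, then 129 per group per facility after 5% loss, and 516 in total. The section goes on to say that this size will "detect a 20% improvement in cumulative weight gain at age 28 days at 95% confidence level and 80% power" (control mean 25%, SD 10%), and will detect a halving of BBAT scores below 7 from 30%, also with 80% power.

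Section 8.14 opens its primary analysis with "For the primary outcomes of average weight loss and weight gain as a proportion of birth weight" and assigns two-sided independent-samples t-tests to them. No clustering term appears. A stratified analysis within each hospital is also planned.

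**The concern.** A design effect above 1 states that observations are correlated in a way that reduces the information in the treatment comparison. The protocol names no such correlation. Dyads are randomised one by one, each dyad contributes one infant, and blocking within facility places both arms in each hospital, so differences in level between hospitals largely cancel from the comparison. Section 8.14 then analyses the weight outcomes as independent.

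Sections 8.9 and 8.14 therefore rest on different views of the data. If the observations are independent, the factor of 2 accounts for half of the 516 dyads without a stated reason, and the stated powers do not describe the trial. If a design effect of 2 is real, the t-test understates the standard error and rejects too often. An ethics committee or DSMB cannot tell from the text which is meant.

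**Working it through.** **Inputs (all from 8.9 unless noted).** Weight loss: control mean 6%, SD 3.6%, difference 25% of 6% = 1.5 points. Weight gain: control mean 25%, SD 10%, difference 20% of 25% = 5 points. BBAT below 7: 30% against 15%. Two-sided alpha 0.05; DE 2.0; loss 5%; 1:1 allocation (8.1).

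**1. Reproduce the plan's sample size.**
- Formula without DE: (1.96 + 1.28)² × 2 × 3.6² / 1.5² = 120.9 per group; 122 with exact critical values and rounding up.
- Times 2.0: 241.9 from the rounded critical values, or 122 × 2 = 244. The plan's 244 reproduces.
- Loss: 122 / 0.95 = 128.4, so 129 per group per facility; 129 × 4 = 516. This also reproduces.

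**2. Power at 244 analysed per arm.** With DE = 2.0 the effective size is 244 / 2 = 122 per arm. The two means use the noncentral t distribution with noncentrality (difference / SD) × √(n/2); BBAT uses the pooled two-proportion formula.

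| Outcome | Stated | DE = 2.0 (n = 122) | DE = 1 (n = 244) |
|---|---|---|---|
| Weight loss, 1.5 / 3.6 | 90% | 90.0% | 99.6% |
| Weight gain, 5 / 10 | 80% | 97.3% | >99.9% |
| BBAT, 30% v 15% | 80% | 80.5% | 97.9% |

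A normal approximation gives 90.2% and 97.4% in place of 90.0% and 97.3%, which changes nothing.

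**3. The weight-gain figure.** The number needed for 80% power is about 64 per arm by the t distribution (63 by the normal approximation). With DE = 2.0 that is 128 (or 126), against 244 available. So 80% is not the power at this size under either value of DE.

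**4. The BBAT figure.** The number needed for 80% power is 120.5, so 121 per arm, or 242 with DE = 2.0. This agrees with 244.

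**5. Size needed without the design effect.** For 90% power on weight loss: 122 per arm analysed, 129 per arm enrolled, 258 in total, which is 516 / 2. The other two outcomes would then have the powers in the DE = 2.0 column (97.3% and 80.5%).

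**6. If a design effect of 2 were real and ignored in the t-test.** The true standard error would be √2 times the one used, so the type I error at a nominal 5% is 2 × (1 − Φ(1.96 / √2)) = 0.166, about 16.6%.

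**The case against.** Several points on the other side are sound and limit what can be claimed.

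- **The arithmetic is not at fault for two outcomes.** A reader might infer that all three stated powers are wrong, or that the size is twice what the plan's own formula requires. The documents do not support that. The printed formula includes DE, and with DE = 2.0 it gives 244, 90% for weight loss and 80% for BBAT. The figures depart from the design only once the factor is removed. Weight gain alone fails both ways, and DE does not explain that gap.
- **DE = 1 is not proven.** Blocking by facility removes facility differences only. Lay KMC workers support one arm (8.6), and sites were chosen partly for the feasibility of keeping the two groups of mothers apart (8.2). Clustering by worker or ward can arise in an individually randomised trial. This stands as a possibility; the protocol neither states it nor gives an ICC.
- **The surplus may have a purpose.** About 122 per group in each facility is what one hospital alone needs for 90% power on weight loss, and 8.14 plans within-hospital analyses. But 8.9 calls the factor a design effect and states no such aim.
- **The error is conservative if DE is 1.** Doubling n is equivalent to tolerating an SD of 3.6 × √2 = 5.1%, which is some protection because the 3.6% comes from a community pilot and this trial runs in hospitals. The weight-gain wording can also be read as a floor, which 97% meets.
- **The 16.6% is conditional.** It applies only if DE = 2 is real and the detailed analysis plan, which 8.14 says will follow, also ignores it. The t-tests are specified for the weight outcomes only, so the conflict with 8.14 does not extend to BBAT.

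None of these points supplies the missing justification for 2.0.

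**Conclusion.** The point holds as an inconsistency between the sample-size assumption and the stated design and analysis, together with one power figure that does not reproduce. Section 8.9 assumes a design effect of 2.0 without a source; 8.1, 8.5 and 8.14 describe individually randomised dyads and, for the weight outcomes, an analysis without clustering.

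Taking the design and analysis as described, the stated powers of 90%, 80% and 80% are about 99.6%, over 99.9% and 97.9%, and half of the planned enrolment would meet the weight-loss target. Keeping DE = 2.0, only the weight-gain power is out, at 97.3% against 80%.

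It would be wrong to conclude that the trial is underpowered. If DE is 1, the consequence is an unexplained doubling of enrolment and understated power. A threat to validity arises only if the clustering is real and the analysis ignores it. The figures rest on the means, SDs and BBAT rate assumed in 8.9, a 5% loss, and two-sided alpha of 0.05 for each outcome.

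**What to change.** Choose one of two routes and write it into 8.9.

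1. **No clustering intended.** Remove the design effect. Restate power at 516 enrolled (244 per arm analysed) as about 99.6%, over 99.9% and 97.9% on the stated assumptions. Say that the size is deliberately larger than required, and why: for example, to support within-facility estimates, or a multiplicity correction over the three primary outcomes. With a Bonferroni split over three, power at 244 per arm would still be about 98.6%, 99.9% and 94.5%.
2. **Clustering intended** (for example by KMC worker or ward). Name the source, the expected cluster size and the ICC that lead to 2.0. Replace the plain t-tests in 8.14 with an analysis that accounts for the clustering, and have the detailed analysis plan agree.

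In either case correct the weight-gain power: over 99.9% under route 1, about 97% under route 2 with DE = 2.0.

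Route 1 costs a rewording of 8.9. Route 2 also needs a change to 8.14 and a record of the clustering unit for each dyad. Neither needs more participants, provided that under route 2 the justified design effect does not exceed 2.0.
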